### 10.1.2 Primary Efficacy Analysis

The primary analysis is a mixed effects model, repeated measures (MMRM) analysis of the change from baseline through 24 weeks of log ACR, with the primary treatment comparison at Week 16 (Visit 10). The model will include treatment (at 3 levels: 8 mg/kg CSL346, 16 mg/kg CSL346, and placebo), baseline log ACR, the stratification variable related to the concomitant use of SGLT2i, visit (as a categorical factor), and interactions between visit and each of the other model terms as factors. The primary comparison of interest will be calculated using a contrast of  $0.5 (8 \text{ mg/kg CSL346} + 16 \text{ mg/kg CSL346}) - \text{Placebo}$ . Please see [Section 16.1](#) for the corresponding SAS Code for the MMRM model. Because this is an early development study and the first study in subjects with T2DM, the one-sided alpha level to be employed for this test is 0.10. Estimated treatment effect of individual CSL346 dose levels versus placebo will also be summarized. The treatment comparisons will be expressed as a percent difference in treatments, calculated as  $100\% \times (\text{geometric mean ratio of the treatment comparison} - 1)$ . The covariance matrix structure to be employed in the primary analysis will be an unstructured pattern. In the event of model convergence issue, a Toeplitz heterogeneous structure will be employed. If the model still fails to converge an autoregressive structure ARH(1) will be assumed.

For the purposes of this analysis, baseline will be defined as the geometric mean of the 6 values obtained before treatment (3 values from Visit 3 and 3 values immediately before treatment at Visit 4). For post-treatment, data for ACR will be collected in triplicate. The value to be employed in the analysis of each post-treatment visit will be the geometric mean of the three values. In the event of missing data, the value for a visit will be the average of the values available. There will be only one primary comparison so there is no consideration of adjustment for multiple comparisons. Comparisons of CSL346 dose levels with placebo will be considered exploratory. The primary analysis will be performed using the ITT Analysis Set. That is, the population for which we are estimating the treatment effect is according to the treatment to which subjects were randomized. To facilitate characterization of response, a line graph of ACR will be provided by relative week with the standard error of measurement (SEM) at each time point by treatment, and by treatment and baseline ACR category.

A supplemental analysis will consider the effects of COVID-19 on the primary endpoint. For subjects with treatment discontinuation due to logistical pandemic-related reasons (“Conclusion of Subject Participation” eCRF, reason of “Pandemic Related”), observations

greater than 28 days after last on-schedule SC infusion received will be excluded. For subjects who received no infusions due to logistical pandemic-related reasons, all data will be excluded. For subjects who test positive for COVID-19 infection during the study, observations on or after the diagnosis date will be excluded. If both conditions apply, then data exclusion will begin at (a) 28 days after the last SC infusion or (b) the diagnosis date, whichever is earlier.

An exploratory analysis of the primary endpoint of ACR will be a categorical analysis of the number of subjects showing a gross change in albuminuria status from baseline to Week 16. As noted above, this will compare the number of subjects in each treatment group who improve from macroalbuminuria at baseline (ACR >300 mg/g [33.9 mg/mmol]) regressing to microalbuminuria (ACR >30 and ≤300 mg/g [>3.39 and ≤33.9 mg/mmol]) or normoalbuminuria (ACR ≤ 30 mg/g [3.39 mg/mmol]) OR from microalbuminuria to normoalbuminuria at Week 16. For analysis of a step change in albuminuria status (i.e., from macroalbuminuria or microalbuminuria to normal albuminuria or microalbuminuria to normal albuminuria OR from microalbuminuria to macroalbuminuria) Cochran-Mantel-Haenszel test stratified for SGLT2i will be employed to compare subjects receiving CSL346 versus placebo.

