3.1 Overall Design

This is a prospective, multicenter, randomized, double-blind, placebo-controlled, proof-of-concept study to investigate the efficacy, safety, tolerability, and PK of repeat doses of CSL346 in subjects with DKD and albuminuria receiving SOC treatment. The study will be divided into 4 periods: Screening, Lead-in, Treatment, and Follow-up (Figure 1).

Figure 1 Overall Study Design

ACR = albumin-to-creatinine ratio; IV = intravenous; SC = subcutaneous.

Approximately 100 subjects will be randomized (1:1:2) to receive blinded IP (8 mg/kg CSL346, 16 mg/kg CSL346, or placebo) for 12 weeks. The initial study population will include subjects with T2DM-DKD and preserved renal function (eGFR ≥ 60 mL/min/1.73m²); the first 18 subjects randomized will be followed for at least 4 weeks after their first dose of IP (Visit 4, Day 1), at which point an Independent Data Monitoring Committee (IDMC) will review their safety and PK data. Following this review, inclusion of subjects with eGFR ≥ 45 mL/min/1.73m² (including CKD stage 3A) will be permitted if approved by the IDMC.

Subsequently, after an IDMC review of safety and PK data from the first 36 subjects (at least 8 subjects with eGFR ≥ 45 to < 60 mL/min/1.73m²) followed for at least 4 weeks, inclusion of subjects with eGFR > 20 to < 45 mL/min/1.73m² will be permitted if approved by the IDMC. If inclusion of subjects with eGFR below 60 mL/min/1.73m² is endorsed by the IDMC, the

following targeted sample size(s) will be established for subjects with eGFR in the specified range:

- At least 36 subjects with eGFR < 60 mL/min/1.73m²
- At least 18 subjects with eGFR < 45 mL/min/1.73m²

To achieve these targeted minimums, a restriction may be imposed on the enrollment of subjects with eGFR ≥ 60 mL/min/1.73m² and / or ≥ 45 mL/min/1.73m².

This staged approach to including subjects with increasing degrees of renal impairment (ie, eGFR ≥ 45 and eGFR > 20 mL/min/1.73m²) is designed to mitigate risk to subjects while enabling preliminary assessment of safety and efficacy in the study population that increasingly reflects the target population for phase 3.

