6.2 Randomization Procedures

A randomization scheme will be used to ensure unbiased treatment assignment. Approximately 100 subjects will be randomized to receive 8 mg/kg CSL346, 16 mg/kg CSL346, or placebo in a 1:1:2 ratio via the IRT system. If dose level stopping criteria are triggered (see [Section 3.7.2](#)), randomization of subjects will be limited to the 8 mg/kg CSL346 dose level or placebo. The randomization will be stratified by SGLT2 inhibitor use.

Using IRT, limits will be imposed to ensure that at least 50% of the subjects enrolled in the study will be receiving concomitant treatment with an SGLT2 inhibitor. If enrollment of subjects not receiving SGLT2 inhibitors reaches 50% (ie, 50 subjects), further enrollment in the study may be restricted to allow only subjects receiving an SGLT2 inhibitor.

If inclusion of subjects with eGFR below 60 mL/min/1.73m² is endorsed by the IDMC, target sample size(s) will be established for subjects with eGFR < 60 mL/min/1.73m² and / or eGFR < 45 mL/min/1.73m².

To achieve these targeted minimums, restrictions may be imposed on the enrollment of subjects with eGFR ≥ 60 mL/min/1.73m² and / or ≥ 45 mL/min/1.73m².

Any restriction on enrollment of subjects based on eGFR will be communicated directly to the sites.

To ensure the study blind is maintained, the IRT external service provider will prepare the study randomization code according to the approved randomization specifications. The IRT external service provider will keep the randomization code on file.

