10.1 Sample Size Estimation

The sample size estimation is based on 2 treatment arms because the primary endpoint analyses will compare CSL346 (8 mg/kg and 16 mg/kg combined) with placebo. The planned sample size is 100 subjects with 50 subjects receiving CSL346 (8 mg/kg, n = 25 and 16 mg/kg, n = 25) and 50 subjects receiving placebo. Assuming an SD of 0.65 for the change from Baseline to Week 16 (Visit 10) in ACR following natural log transformation, a sample size of 94 subjects is estimated to provide 85% power to detect a 27% reduction in the geometric mean ACR for CSL346 versus placebo, ie, $\ln(1 - 0.27) = -0.315$ on the natural log scale, using a 1-sided $\alpha = 0.10$. For this study, statistical significance will be achieved with an observed treatment effect of -0.173 on the natural log scale, or approximately -16% when expressed as a percent difference in treatments, depending on the observed variability. The total sample size accounts for an assumed 6% drop-out rate. The actual early discontinuation rate will be assessed throughout the study and up to 124 subjects may be randomized if necessary, to target 94 completed subjects (subjects who received all doses and completed the Week 16 ACR assessment).

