### **4.4 Determination of the Sample Size**

The sample size estimation is based on 2 treatment arms because the primary endpoint analyses will compare CSL346 (8 mg/kg and 16 mg/kg combined) with placebo. The planned sample size is 100 subjects with 50 subjects receiving CSL346 (8 mg/kg, n = 25 and 16 mg/kg, n = 25) and 50 subjects receiving placebo. Assuming a SD of 0.65 for the change from Baseline to Week 16 (Visit 10) in ACR following natural log transformation, a sample size of 94 subjects is estimated to provide 85% power to detect a 27% reduction in the geometric mean ACR for CSL346 versus placebo, i.e.  $\ln(1 - 0.27) = -0.315$  on the natural log scale, using a one-sided  $\alpha = 0.10$ . For this study, statistical significance will be achieved with an observed treatment effect of  $-0.173$  on the natural log scale, or approximately  $-16\%$  when expressed as a percent difference in treatments, depending on the observed variability. The planned total sample size of 100 subjects accounts for an assumed 6% drop-out rate. The actual early discontinuation rate will be assessed throughout the study and up to 124 subjects may be randomized if necessary, to target 94 completed subjects (subjects who received all doses and completed the Week 16 ACR assessment).

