### **8.2.3 Baseline Definition**

Baseline is defined as the most recent, non-missing value before the first IP administration (including unscheduled visits) for all assessments unless otherwise stated. In case of an assessment at the same date as the first IP administration (and only the date for that assessment is available) it will be assumed the assessment was done before IP administration.

For the purposes of the analysis of albumin creatinine ratio, baseline will be defined as the geometric mean of the 6 values obtained before treatment (3 values from Visit 3 and 3 values immediately before treatment at Visit 4). If fewer than 6 values are available, the geometric mean of all the available values will be used for baseline.

Baseline for blood pressure will be the mean of the three values (or all available if fewer than three) collected immediately before the IV loading dose.

Baseline for serum creatinine will be an average of the two samples collected prior to first IP administration (Visit 3 and Visit 4). Baseline eGFR will be calculated based on the baseline

serum creatinine. These calculated baseline eGFR values will be used to define eGFR categories and covariates in statistical analyses.

For soluble tumor necrosis factor receptor 1 (sTNFR1), exploratory circulating and urinary markers, the baseline value will be an average of the two samples collected prior to first IP administration (Visit 3 and Visit 4). [Note: Exploratory circulating biomarkers are defined in [Section 4.1.4](#) as biomarkers of lipid metabolism including but not limited to circulating total cholesterol, triglycerides, high density lipoproteins (HDL), low density lipoproteins (LDL), glycerol, non-esterified fatty acids (NEFA), and ketones. Urinary markers are defined in [Section 10.3](#) as VEGF-A, soluble VEGF receptor 1 (VEGF-R1), kidney injury molecule-1 (KIM-1), neutrophil gelatinase-associated lipocalin (NGAL), clusterin, monocyte chemoattractant protein-1 (MCP-1) and epidermal growth factor (EGF).]

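### The primary ACR model does not adjust for baseline eGFR, although eGFR governs staged entry, the enrolment targets and an a priori subgroup

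*SAP*

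**What the plan says.** **Role of eGFR in the design.** Entry starts at eGFR 60 or above. It can open to 45 or above after IDMC review of the first 18 subjects, and to above 20 after review of "the first 36 subjects (at least 8 subjects with eGFR" from 45 to below 60). Once the IDMC endorses enrolment below 60, minimum targets apply: 36 subjects below 60 and 18 below 45 (Protocol 3.1, 4.1.1). Amendment 2 added only the tier from above 20 to below 45, and only subject to IDMC endorsement. SAP 10.1.4 names four baseline eGFR categories as one of two a priori subgroup analyses of ACR.

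**Randomization.** Protocol 6.2: "The randomization will be stratified by SGLT2 inhibitor use". SAP 4.3 and 8.3 agree, and eGFR is not a stratum.

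**Primary model.** Besides treatment at three levels, SAP 10.1.2 lists "baseline log ACR, the stratification variable related to the concomitant use of SGLT2i, visit (as a categorical factor), and interactions between visit" and each other term. Protocol 10.3.2 and the SAS code in SAP 16.1 match this. None has an eGFR term, and neither do the COVID-19, per-protocol or tipping-point analyses.

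**Covariate statement.** SAP 8.2.3 derives baseline eGFR from the mean of the Visit 3 and Visit 4 serum creatinine values and says that the results "will be used to define eGFR categories and covariates in statistical analyses". It does not say which analyses.

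**The concern.** The plan treats eGFR as important enough to control who enters and when, and to define subgroups for the primary endpoint. It then leaves eGFR out of both devices that would keep it from disturbing the treatment comparison: stratification and covariate adjustment.

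Two things are at stake. First, if change in log ACR depends on baseline kidney function beyond what baseline ACR and SGLT2 inhibitor use explain, that variation stays in the residual and a chance imbalance feeds into the estimate. Second, staged entry ties eGFR to calendar time. Under Protocol 3.7.2 the IDMC may recommend stopping 16 mg/kg, after which new subjects go only to 8 mg/kg or placebo. Subjects with lower eGFR enter later, so the 16 mg/kg arm would hold fewer of them by construction. The primary contrast still gives each dose a weight of 0.5.

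**Working it through.** **Inputs from the documents.** One-sided alpha 0.10 ("the one-sided alpha level to be employed for this test is 0.10"); difference 0.315 on the log scale, a 27% reduction; SD 0.65 ("Assuming a SD of 0.65 for the change from Baseline to Week 16 (Visit 10) in ACR"); 94 evaluable subjects, taken as 47 pooled CSL346 and 47 placebo; 100 randomized, 50 and 50; eGFR minimums of 36 and 18.

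**Assumptions (not in the documents).** The partial R² of baseline eGFR with Week 16 change in log ACR, given the terms already in the model; and the difference D in log ACR change between lower and higher eGFR. The SD of 0.65 is treated as the residual SD of the present model.

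**1. The plan's own figures.** SE = 0.65 × √(2/47) = 0.134. Noncentrality = 0.315 / 0.134 = 2.35. With 92 df, power is 85.5% (normal approximation 85.7%), against the stated 85%. The significance threshold is t(0.90; 92) × SE = 0.173, or −16%, as stated. These reproduce without any eGFR term.

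**2. Precision gained by adjusting.** Residual SD = 0.65 × √(1 − R²), with one more df used.

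| Assumed partial R² | Residual SD | Power at N = 94 | Threshold | N for 85% (normal approx.) |
|---|---|---|---|---|
| 0 | 0.650 | 85.5% | 0.173 | 92 |
| 2% | 0.643 | 86.0% | 0.171 | 90 |
| 5% | 0.634 | 86.8% | 0.169 | 88 |
| 10% | 0.617 | 88.2% | 0.164 | 84 |

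For a split at 60 with 36% below it, R² = 0.36 × 0.64 × D² / 0.65². D = 0.2, 0.3 and 0.4 give 2.2%, 4.9% and 8.7%.

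**3. Chance imbalance.** Let X be the number of subjects below eGFR 60 in the pooled CSL346 arm: hypergeometric, 36 of 100, 50 drawn (SGLT2i strata and any blocking ignored). The gap in share is (2X − 36)/50.
- SD of the gap: 9.7 percentage points.
- Gap of at least 10 points (X ≤ 15 or X ≥ 21): 30%.
- Gap of at least 20 points (X ≤ 13 or X ≥ 23): 6%.
- A 25-subject dose arm would hold 5 to 13 such subjects (95% range; expected 9).

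The shift in one trial's estimate is gap × D. For D from 0.1 to 0.5, a 10-point gap shifts it by 0.01 to 0.05 and a 20-point gap by 0.02 to 0.10, the latter being 6% to 32% of 0.315.

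**4. Validity.** In 20,000 simulated trials per setting (47 against 47, 36% below 60, D = 0, 0.2, 0.4, 0.6), one-sided type I error was 0.099 to 0.103 without eGFR and 0.097 to 0.104 with it. Power without eGFR was about 85.5% throughout. With it, power was 85.1%, 85.7%, 87.9% and 90.5%.

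**5. If 16 mg/kg were stopped.** Illustration, assuming a stop after 36 subjects (9, 9 and 18), 64 more randomized, and 18 of those below eGFR 45:
- Later ratio 1:1. Placebo 9/50 = 18%; 8 mg/kg 9/41 = 22%; 16 mg/kg 0%. Primary contrast: 0.5 × (22 + 0) − 18 = −7 points.
- Later ratio 1:2 (8 mg/kg to placebo). Placebo and 8 mg/kg each about 20%; 16 mg/kg 0%. Primary contrast: 0.5 × (20 + 0) − 20 = −10 points.

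16 mg/kg against placebo is off by 18 to 20 points. With D from 0.1 to 0.5, that comparison shifts by 0.02 to 0.10, and the primary contrast by about half of that or less.

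**The case against.** The best defence is that omitting a prognostic covariate is a legitimate choice in a 100-subject phase 2a study. The model already adjusts for baseline log ACR and the stratification factor, SAP 10.1.1 explains why SGLT2i is the modifier of interest, and type I error and stated power hold without eGFR. The gain is zero if eGFR is not prognostic. Subgroup models, scatterplots and baseline tables will make an imbalance visible. All of this stands, and it limits the point to efficiency and robustness. The subgroup models do not replace adjustment, though: at the target minimums their power for the design effect is about 57% (36 subjects) and 40% (18 subjects), before dropout, and no treatment-by-eGFR test is planned.

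A reader might also infer more than the documents support:
- *That staged entry itself biases the comparison.* With concurrent 1:1:2 randomization at every stage, a changing eGFR mix causes no systematic imbalance. That needs a stop of 16 mg/kg, and nothing shows that one occurred.
- *That SAP 8.2.3 promises eGFR in the ACR model.* It names no model. Section 10.2 gives it a use, since the eGFR MMRM takes its own baseline as covariate. The sentence is unspecific but not contradicted.
- *That adjustment would strengthen the IDMC's decision to open lower eGFR tiers.* Those reviews concern safety and PK, which an ACR covariate does not affect.
- *That the remedy is to stratify by eGFR.* This could help only subjects not yet randomized, and the documents do not show that any remained at SAP version 3.0.

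**Conclusion.** The point holds as a recommended improvement, not as an error in the test, the alpha or the sample size. Baseline eGFR structures enrolment and a primary-endpoint subgroup, yet no ACR analysis adjusts for it.

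The likely loss is modest: 0 to 2.7 percentage points of power for a partial R² from 0 to 10%, a range that is assumed. The protection against imbalance matters somewhat more. The 30% and 6% chances assume that the target of 36 subjects below eGFR 60 is exactly met, and it applies only if the IDMC endorses enrolment below 60. How far such a gap moves the estimate depends on D, also assumed. The dose-stopping case is a contingency. There an eGFR term would remove only part of the problem, because other calendar-time differences between 16 mg/kg and later controls would remain, and a linear term would extrapolate where that arm has few subjects.

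**What to change.** Before the unblinding for the interim analysis described in SAP 4.5.1:

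1. Add continuous baseline eGFR and its interaction with visit to the primary MMRM in SAP 10.1.2 and to the MODEL statement in 16.1. The value is already derived in 8.2.3. The treatment ESTIMATE statements need no change, since no treatment-by-eGFR term is added.
2. State in SAP 8.2.3 which models use baseline eGFR as a covariate.
3. Record the added covariate in SAP Section 5, because Protocol 10.3.2 lists the model without it.

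If the sponsor prefers to keep the present primary model, the minimum is to pre-specify the eGFR-adjusted model as a sensitivity analysis. The cost is SAP wording and one parameter per visit, six over Weeks 2, 4, 8, 12, 16 and 24. If eGFR is not prognostic, nothing is gained and precision falls negligibly (simulated power 85.1% against 85.5%). Chosen after unblinding, the adjustment would be post hoc.

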10.3.2 Efficacy Analyses

Primary Endpoint

The primary analysis is a mixed effects model, repeated measures (MMRM) analysis of the change from Baseline through 24 weeks of log ACR, with the primary treatment comparison at Week 16 (Visit 10). The model will include treatment (at 3 levels: 8 mg/kg CSL346, 16 mg/kg CSL346, and placebo), Baseline log ACR, the stratification variable related to the concomitant use of SGLT2 inhibitors, visit (as a categorical factor), and interactions between visit and each of the other model terms as factors. The primary comparison of interest is a contrast of 0.5 (8 mg/kg CSL346 + 16 mg/kg CSL346) – Placebo. Estimated treatment effect of individual CSL346 dose levels versus placebo will also be summarized. The treatment comparisons will be expressed as a percent difference in treatments, calculated as $100\% \times (\text{geometric mean ratio of the treatment comparison} - 1)$. For the purposes of this analysis, Baseline will be defined as the geometric mean of the 6 values obtained before treatment (3 values from Visit 3 and 3 values immediately before treatment at Visit 4). The procedure for determining the covariance model for log ACR residuals will be defined in the SAP. There will be only 1 primary comparison so there is no consideration of adjustment for multiple comparisons. Comparisons of CSL346 dose levels with placebo will be considered exploratory. The primary analysis will be performed using the ITT Analysis Set.

Two sensitivity analyses will be considered for the primary endpoint. The first such analysis considers the effects of COVID-19 on the primary endpoint. For subjects with treatment discontinuation / interruption due to logistical pandemic-related reasons, observations greater than 28 days after last on-schedule SC infusion received will be excluded. For subjects who received no infusions due to logistical pandemic-related reasons, all data will be excluded. For subjects who contract COVID-19 infection during the study, observations on or after the infection date will be excluded. If both conditions apply, then data exclusion will begin at (a) 28 days after the last SC infusion or (b) the infection date, whichever is earlier. The second sensitivity analysis is a tipping point analysis that will employ multiple imputation for missing data using multiple regression to provide multiple complete data sets. The same MMRM model will be used to analyze the complete data set.

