### **Study Treatment Discontinuation or Study Discontinuation**

Subjects who have either study treatment discontinuation or study discontinuation due to

COVID-19 will have the reason captured in the electronic case report form (eCRF). On the appropriate eCRF form to record either study medication discontinuation (“End of Treatment” form) or study discontinuation (“Conclusion of Subject Participation” form), a reason will be selected which includes a field for descriptive text. The reason can be either “Withdrawal by Subject”, “Physician Decision” or “Other”. The associated free text field entry will include “COVID-19”. When either treatment or the study is discontinued due to an AE or death, the specific corresponding AE is collected. Discontinuations due to COVID-19 adverse events (AE) will then be identified based on whether the Medical Dictionary for Regulatory Activities (MedDRA) code for the AE is included in the COVID-19 standard MedDRA query (SMQ) (Narrow).

Cases of study treatment discontinuation or study discontinuation due to COVID-19 will be included in the summary of subject disposition.

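### The SAP's COVID-19 analysis looks for treatment discontinuation on the study-exit form, under a reason SAP 7.1 does not list, and omits the protocol's treatment interruptions without declaring it

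*SAP*

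**What the plan says.** Protocol 10.3.2 defines a COVID-19 sensitivity analysis of the primary endpoint. Its logistical rule opens: "For subjects with treatment discontinuation / interruption due to logistical pandemic-related reasons". ACR values more than 28 days after the last on-schedule SC infusion are then excluded.

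SAP 10.1.2 carries this over as a supplemental analysis, but its rule opens: "For subjects with treatment discontinuation due to logistical pandemic-related reasons". It adds in brackets how these subjects are found: "Conclusion of Subject Participation” eCRF, reason of “Pandemic Related". Two further rules follow with no form or code attached: "For subjects who received no infusions due to logistical pandemic-related reasons, all data will be excluded", and "For subjects who test positive for COVID-19 infection during the study, observations on or after the diagnosis date will be excluded".

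SAP 7.1, under Study Treatment Discontinuation or Study Discontinuation, describes the data collection. It separates "study medication discontinuation (“End of Treatment” form) or study discontinuation (“Conclusion of Subject Participation” form". On the reasons it says "The reason can be either “Withdrawal by Subject”, “Physician Decision” or “Other", and then "The associated free text field entry will include “COVID-19". Discontinuations due to a COVID-19 adverse event are found separately, through MedDRA coding.

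SAP Section 5 lists two changes from the protocol: the Per-Protocol set definition and the removal of VEGF-B. The COVID-19 rule is not mentioned.

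**The concern.** The 28-day cut-off matters most for subjects who stop or skip investigational product and still provide urine samples. Someone who leaves the study soon after the last infusion has few or no later values to exclude. Someone who stops dosing and keeps attending does have them. The second kind of subject has not left the study, so a study-exit form is the wrong place to look.

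Protocol 9.1.3 asks sites to keep subjects in follow-up after product is stopped for an adverse event of special interest. The primary estimand in SAP 10.1.1 uses all data regardless of discontinuation. Such subjects can therefore be expected in the data.

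If they are not selected, their values stay in and the supplemental estimate lies closer to the primary estimate than the protocol intended. That agreement could be read as evidence that pandemic disruption made little difference, when it partly reflects the selection rule.

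**Working it through.** The point rests on comparing passages, with one piece of day arithmetic. The documents give no figure for pandemic-related cases, so there is no plan figure on this point to reproduce.

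**1. Form.** The event to be found is treatment discontinuation.
- SAP 10.1.2 source: *Conclusion of Subject Participation*.
- SAP 7.1 source for stopping treatment: *End of Treatment*.
- SAP 7.1 use of *Conclusion of Subject Participation*: leaving the study.

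A subject who stops product at Week 8 for logistical reasons and attends through Week 24 has discontinued treatment but not the study. No reason for leaving early applies, whatever the form's code list contains.

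**2. Reason.**
- SAP 10.1.2: *Pandemic Related*.
- SAP 7.1: one of three reasons, with COVID-19 in free text.

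The two specifications do not overlap. If 7.1's list is the one in use, the discontinuation rule read literally selects no one.

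**3. Event.**
- Protocol 10.3.2: discontinuation or interruption.
- SAP 10.1.2: discontinuation only.

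The SAP keeps the reference to the last on-schedule infusion, which fits interruptions, so the omission looks unintended.

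**4. Does an interruption reach the primary time point?** Study days are from the Schedule of Assessments: Week 8 infusion Day 57, Week 12 infusion Day 85, primary ACR Day 113.
- All infusions given: 113 − 85 = 28 days, not more than 28.
- Week 12 infusion missed: 113 − 57 = 56 days, more than 28.

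If the Week 12 infusion is missed for logistical reasons, the protocol excludes the Week 16 value. If the miss is recorded as an interruption, the SAP rule keeps it.

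**5. Scale, for illustration only.** Assume a share s of the 94 evaluable subjects should lose their Week 16 value, split equally between pooled CSL346 and placebo. From SAP 4.4: difference 0.315, SD 0.65, one-sided alpha 0.10, so n = 47(1 − s) per group and

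power = Φ(0.315 / (0.65 × √(2/n)) − 1.2816).

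At s = 0, 0.65 × √(2/47) = 0.134 and 0.315/0.134 = 2.349; Φ(2.349 − 1.282) = 85.7%, which reproduces the plan's 85%.

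| s (assumed) | Subjects (94 × s) | Power |
|---|---|---|
| 2% | about 2 | 85.2% |
| 5% | about 5 | 84.3% |
| 10% | about 9 | 82.8% |
| 20% | about 19 | 79.4% |

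This is a two-group approximation, not the MMRM. It shows the precision that correct selection would cost under each assumption. It does not estimate bias or the number of subjects missed.

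**The case against.** The strongest reply is that the case report form was not available for review. SAP 10.1.2 names a specific reason label, which may be a real option, in which case 7.1 is the text that is wrong. That is fair, and the documents cannot settle it. The two sections must still be reconciled, and the form mismatch and the missing interruptions remain.

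Second, the Per-Protocol sensitivity analysis (SAP 10.1.3 and 16.7) already lists a missed intermittent dose as a factor. For subjects with fewer than four doses it excludes data from the last dose plus 4 weeks plus 1 day. So missed doses and early stopping are examined on the same endpoint with nearly the same cut-off. That reduces the consequence. But it applies whatever the cause and alongside many other exclusions, so it does not isolate the pandemic as protocol 10.3.2 intends.

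Third, SAP 7.1 requires summaries of COVID-19 missed visits, missing assessments and discontinuations, so a reader would see the disruption itself. This stands, but those tables do not show its effect on ACR.

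A reader might go further and infer that the analysis would exclude almost nobody for logistical reasons and would falsely show no pandemic effect. The documents do not support that. SAP 7.1 does name the cited form, though for another purpose. The no-infusion and positive-test rules work without the code. The reason may exist on the form. No rate of pandemic-related discontinuation or interruption is given.

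**Conclusion.** The point holds for one rule in one supplemental analysis. For logistical treatment discontinuation, SAP 10.1.2 points to the wrong form under SAP 7.1 and to a reason 7.1 does not list. It also omits the interruptions in protocol 10.3.2 without declaring the change. The rule could miss subjects who stop or miss product for logistical pandemic reasons but remain in follow-up, and so could understate the pandemic's effect in this analysis.

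The number missed is unknown and could be zero if no such subjects occur. The literal result that the discontinuation rule selects no one rests on 7.1's reason list being the one in use. The finding on interruptions does not depend on that. The no-infusion rule, the positive-test rule and the primary ITT analysis are unaffected. The change should be made, but the primary conclusion does not depend on it.

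**What to change.** Reword the logistical rule in SAP 10.1.2:

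- **Discontinuation.** Select from the *End of Treatment* form using 7.1's reasons and COVID-19 free text. That text alone does not separate logistical from other COVID-19 reasons, so confirm logistical cases at the blinded data review. If the form really carries *Pandemic Related*, state the actual form and code and correct 7.1 to match.
- **Interruption.** Restore it as in the protocol. Identify it from dosing records together with the COVID-19 flag on the Visit Status form and COVID-19 protocol deviations. The Visit Status form alone is not enough: it is described as recording missed visits and visit modality, not infusions missed at a visit that was attended. If interruptions are left out on purpose, declare and justify that in Section 5.

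The cost is about one SAP paragraph, a possible correction to 7.1, and a case check at a data review meeting already planned. The SAP describes these sources as collected for other purposes, so no new data collection appears necessary. The change is best made before the unblinding for the interim analysis.
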